Patients living in board and care facilities or other residential facilities have little control of their food options and therefore are faced with challenges involving increasing whole grains or fruit/vegetable consumption. They are also served foods high in refined carbohydrates and saturated fats. The LB coach/dietitian can make suggestions, according to what the individual consumes often and illustrate how that individual could add a healthier option to a certain part of their meal regimen (i.e., if an individual drinks 16 oz of soda at 3:00pm everyday, suggest having either a diet soda or a fruit serving with a cup of water as a snack). One or two small, attainable nutrition goals are set for the patient to follow for one week only. The patient writes in their food/exercise journal and includes, to the best of their ability, everything they eat and drink along with what type of physical activity they participate in, including specific amounts and times of the day for one week. The patient focuses on achieving realistic, small goals set with the LB coach/dietitian and these goals are reviewed weekly for the first 8 weeks of the study, and then monthly thereafter. At each session with the lifestyle balance coach the veteran establishes realistic goals that are written down and then followed up upon at the next appointment. Adherence to the goals will be checked at the next appointment by the lifestyle balance coach.

Slim-Fast Criteria:

Patients will be offered Slim-fast meal replacement shakes/bars as an option should they fall under the following criteria:

- a) The patient believes they could replace one meal per day with a Slim-fast shake/bar without eating any other food within 2 hours of shake/bar consumption.
- b) The patient agrees to turn in a food/exercise journal illustrating how the meal replacement shake/bar was used.
- c) The patient loses at least 1-2 lbs in the first week of using the meal replacement shake/bar.

3. Physical Activity: All patients randomized to the multi-modal, Lifestyle Balance Program will be asked to increase physical activity. Prior to increasing physical activity (with a goal of 30 minutes of walking per day), patients will have physical exams. Risk stratification for ETTs (exercise tolerance test) will be done for all veterans entering the protocol according to the recommendations of the American College of Sports Medicine(64, 65). All veterans with moderate or high risk stratification who are interested in doing vigorous exercise or any veterans reporting cardiac symptoms will be given an exercise tolerance test. Patients who required an ETT prior to entering the protocol will repeat an ETT at conclusion of the study period. The information obtained from the repeat ETT will help assess for changes in functional capacity, cardiovascular fitness, and physiologic response to exercise in addition to reassuring safety for the veteran to continue a self-directed longer term fitness program at the conclusion of the study protocol period. This goal should be set for individuals that agree to increase physical activity, but if the patient is not motivated and/or overwhelmed with having more than one goal, the focus will begin with the nutrition goal and a recommendation of a gradual increase in physical activity will be set. Also, a goal to increase in physical activity could be something very small (i.e., patient went from driving to the store to walking to the store, patient started using the stairs instead of the elevator). Lifestyle change should be very gradual. A habit is formed over time, therefore LB coaches/dietitians/health professionals should be sensitive to an individual’s ability to make changes, following the Stages of Change Model and assessing where the patient places on the Stages of Change Model is important.

Ultimately the goal however, is that all patients randomized to the multimodal, Lifestyle Balance Program will exercise 30 minutes per day for at least 5 days per week. As walking is the easiest exercise to encourage pedometers will be provided. We will also encourage patients to participate in other types of exercise and we will schedule supervised exercise activities at our PRRC as well as the Wellness Program run by [name]. Classes will be run by the Lifestyle Balance group leaders and/or an exercise instructor. Physical exams and ETTs will be done to assure safety prior to beginning exercise when patients have significant cardiovascular risk factors or history of previous myocardial infarction. [name] has initiated yoga and tai chi classes at the West Los Angles facility as part of the newly developed PRRC (psychosocial rehabilitation and recovery center). She is also part of a committee that will be establishing these types of classes at Sepulveda VAMC and LAAC. The Long Beach facility has a large campus ideally suited for walking, as does the Sepulveda and West Los Angeles sites. The LAAC campus is in downtown Los Angeles one block away from a large park that patients can be encouraged to walk around.

4. Food and Exercise Diaries: Patients in the Lifestyle Balance Program will be asked to maintain food and exercise diaries to discuss individually on a weekly basis with their case manager for the first 8 weeks and then once per month.

5. Knowledge Quiz: Patients will be asked to answer questions about their knowledge of healthy eating habits and nutrition. Questionnaires will be given at the beginning and end of the initial 8 weeks of classes, at 6 months and at 12 months

6. Class Schedule: Patients in the behavioral program will participate in 16 classes over approximately the first 2 months (2 classes per session). The classes on Lifestyle Balance (based largely upon the “Lifestyle Balance classes” utilized in the Diabetes Prevention Program) (42) are the following:

Welcome to the Lifestyle Balance Program	Fat Facts
How Antipsychotic Medications Affect Me	What’s On Today’s Table
Becoming Active: A Way of Life	Take Charge of What’s Around You
Mindful Eating	Tip the Calorie Balance
Moving those Muscles	Your Food Away from Home
Weighing the Risks	Delicious Decisions
You Can Manage Stress-Mindfulness, yoga, taichi	Variety on Your Plate
Carbs: Simply Complex	Ways to Stay Motivated

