C. Long Term Objectives: 1) To decrease the long term risks associated with obesity such as coronary artery disease and diabetes in the SMI population. 2) To promote recovery, improve mental health, quality of life, and treatment adherence, and to decrease utilization of hospital resources by improving the overall medical and psychiatric condition of these patients. 3) To create a user-friendly intervention program that is easy to disseminate and implement and can be provided by any motivated health care provider in any mental health setting. 4) Finally, we wish to network with other mental health providers and create an educational website that will allow us to disseminate the program further outside of our 4 sites. Specifically, we think this will be helpful to ultimately disseminate this manualized long term weight loss program to other mental health programs such as PRRCs that are being established by the Uniformed Services Package throughout the country (3).

D. Hypotheses

1. Primary Hypotheses:

a) Veterans with SMI at four different sites with antipsychotic associated obesity who participate in the 12-month multi-modal, MOVE-like, intervention that includes classes of the Lifestyle Balance Program, and individualized lifestyle balance coaching, will gain more knowledge (i.e., greater change scores on before/after survey test instrument) about general health issues (e.g., nutrition, importance of exercise, etc.) than a control group receiving "usual psychiatric care."

b) Subjects randomized to active treatment in the 12-month, Lifestyle Balance Program will make more objective lifestyle changes (as measured by exit interviews, food and exercise diaries, fidelity assessments) than those in the usual psychiatric care group.

c) Subjects who participate in the 12-month multi-modal Lifestyle Balance Program will achieve better cardiovascular (e.g., sustained weight loss, better glucose tolerance, improved lipid profiles) and mental health (e.g., improvements in recovery from mental illness, improvement in biopsychosocial/spiritual wellness [measured by the WHO-QOL BREF and the BPSS], general measures of psychopathology, subjective quality of life, etc) outcomes than the control group.

2. Secondary Hypotheses:

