C. Informed Consent: Patients will be asked to give written informed consent at the beginning of the study. The participation of subjects with severe treatment refractory schizophrenia and other vulnerable populations in research protocols has led to some controversy over these individuals' abilities to give meaningful consent (14). We currently employ a rigorous and interactive test experience to aid subjects in learning the informed consent material and to assist us in determining subjects' level of understanding. We will be using an informed consent quiz in this protocol. We will also be using a teaching device, videotape that can assist subjects in understanding the consent process and become active learners in consenting to research. Because it is a long-term study we will re-check patients' understanding of their protocol participation on an ongoing basis (at least every 6 months) using our informed consent quiz.

D. Lifestyle Balance Treatment Procedures: All scales, the manual for the class participants, and a portion of the training manual for the Lifestyle Balance coaches including the adherence "toolbox" are included as appendices to this application (the full materials can be accessed at www.bsc.gwu.edu/dpp/manuals.htmlvdoc). Because some of the materials utilized in the original diabetes prevention program in 1996 are outdated (e.g the food pyramid has been revised) we have updated these materials during our current study and those new updated materials will be available at the study website which will be developed for this project. 120 patients will be randomized to either "usual care" or to a behavioral weight loss program. Those patients randomized to the behavioral weight loss program (Lifestyle Balance Program) will do the following:

1. Behavior therapy procedures. Three evidence-based, behavior therapy interventions will be incorporated into the Lifestyle Balance Program: (a) motivational interviewing, (b) contingency contracting and (c) social skills training for promoting optimal implementation of dietary and exercise assignments.

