a) SMI patients with antipsychotic associated obesity who participate in a behavioral intervention that includes classes on Lifestyle Balance will gain more knowledge (i.e., greater change scores on before/after survey test instrument) about general health issues (e.g., nutrition, importance of exercise.) than a control group receiving “usual psychiatric care”.

b) SMI patients with antipsychotic associated obesity who participate in a behavioral intervention program will achieve better cardiovascular (e.g., sustained weight loss, better glucose tolerance, improved lipid profiles, and improvement in other biological measures, e.g. insulin and c-reactive protein) and mental health (e.g., improvements in general measures of psychopathology, subjective quality of life, etc) outcomes than the control group. A larger proportion of patients who take the Lifestyle Balance classes will actually make lifestyle

changes (objectively measured by food and exercise diaries) than patients in the usual care group given ordinary counseling.

c) A larger proportion of patients who take the Lifestyle Balance classes will actually make lifestyle changes (objectively measured by food and exercise diaries and exit interviews) than patients in the usual care group given ordinary counseling. Analysis plan: For all hypotheses concerning the effects of the treatment program use analysis of repeated measures using the assessments at baseline, 8 weeks, 6 months, and 12 months. These analyses will provide information about maintenance of treatment effects. We will use a mixed general linear model with timepoints nested within patients. For hypothesis (c) we will adapt the mixed general linear model to dichotomous data by using a logistic link function to model the likelihood of life style changes. We will include all patients with at least one post-baseline data point in the analysis to maximize power. We will also consider the appropriateness of linear growth curve mixed effects models, i.e., fitting an intercept and linear slope for each treatment group as fixed effects, and separate intercepts and linear slopes for each patient as random effects. Analyses of linear trends over time with a single df effect are often more powerful tests of differences in trends than multiple df profile contrasts across the separate time points.

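### The primary lifestyle-change comparison rests chiefly on food and exercise diaries, but the arm-specific text assigns diaries only to the program arm and leaves usual care unstated

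*Combined protocol and SAP*

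**What the plan says.** The lifestyle-change hypothesis appears three times, with different measures.

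- I.D.1(b): program patients will "make more objective lifestyle changes (as measured by exit interviews, food and exercise diaries, fidelity assessments" and so on, compared with usual care.
- V.N, Statistical Plans, hypothesis (b): a larger proportion will change, "objectively measured by food and exercise diaries) than patients in the usual care group given ordinary counseling".
- V.N, Statistical Plans, hypothesis (c): the same comparison, "objectively measured by food and exercise diaries and exit interviews".

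For treatment-effect hypotheses the analysis plan is to "use analysis of repeated measures using the assessments at baseline, 8 weeks, 6 months, and 12 months". For (c) the mixed model is adapted to a yes/no outcome "by using a logistic link function to model the likelihood of life style changes". On who is analysed: "We will include all patients with at least one post-baseline data point in the analysis to maximize power".

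Diary keeping is described in V.D, in a list introduced by "Those patients randomized to the behavioral weight loss program (Lifestyle Balance Program) will do the following". Item 4 of that list is the diary instruction: "Patients in the Lifestyle Balance Program will be asked to maintain food and exercise diaries to discuss individually on a weekly basis". Item 2 makes the food and exercise journal part of goal-setting with the coach or dietitian. V.E (usual care) mentions modest counseling, weighing, a knowledge questionnaire and a photograph. It does not mention diaries.

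**The concern.** A between-arm comparison needs the same outcome measured in the same way in both arms. Here the main measure is also a component of the intervention: the diary is what the coach and patient discuss and set goals from. If usual care keeps no diary, a primary hypothesis has no comparable control data from its main source. If usual care keeps one, the plan should say so, because the answer decides whether the stated model can be fitted to diary data at all.

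The mixed model's tolerance of missing data would not help. An outcome that was never collected in one arm is absent by design. Imputing it would mean carrying over relations seen in the program arm.

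**Working it through.** The plan gives no figure for this outcome; its power section works through a continuous outcome only, with weight as the example. The check is therefore a comparison of passages, followed by one short calculation.

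**Step 1. Which named measure covers the four analysis times?**

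| Measure | I.D.1(b) | Stat. Plans (b) | Stat. Plans (c) | Schedule of Events |
|---|---|---|---|---|
| Food and exercise diary | named | named | named | every visit |
| Exit interview | named | – | named | week 52 only |
| Fidelity assessment | named | – | – | months 0, 6 and 12 |

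Only the diary is in every statement and at every analysis time. The schedule does not state an arm for any of the three.

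**Step 2. Who keeps diaries?**

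Pointing to the program arm only:
- V.D items 2 and 4 place the diary within program procedures.
- V.E restates the knowledge questionnaire and the photograph, both also listed in V.D, but not the diary.
- The schedule's diary row carries rater code RD. So do the rows for classes, booster classes, goal sheets, additional interventions and caregiver sessions, and V.E withholds the classes from usual care.

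Leaving it open:
- The schedule has no arm column.
- V.H says that patients will be asked for a diary, without naming an arm.
- II.C and IV.C describe diaries as part of the group's routine clinical care.
- V.E is not a full list of assessments; it also omits the BPRS and the laboratory tests.

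**Step 3. What follows from each reading?**

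- *Program arm only.* Under the inclusion rule, a usual-care patient with no diary has no post-baseline diary value to enter. The exception is a usual-care patient who takes up the program after 6 months (V.E and V.L allow this). Such a patient might have a late diary, but it would come from a selected patient who is by then receiving the intervention. It is not a usual-care measurement.
- *Both arms, collected alike.* The comparison can be made. What remains is to align the three lists of measures and to state the yes/no rule.

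**Step 4. Size of the bias in the worst case.** Suppose an absent diary were scored as no change. Let *p* be the true change rate, equal in both arms, and *c* the share of changes captured by a usable diary.

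False difference = *p* × *c*(program) − *p* × *c*(usual care). With *c*(usual care) = 0 this is *p* × *c*(program).

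| Assumed *p* | *c*(program) = 100% | 80% | 50% |
|---|---|---|---|
| 10% | 10 points | 8 | 5 |
| 30% | 30 points | 24 | 15 |
| 50% | 50 points | 40 | 25 |

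All values of *p* and *c* are assumptions; the documents give neither. IV.E.4 does report that diaries were difficult for some veterans, so full capture is unlikely.

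**The case against.** The strongest reply is that this is an ambiguity and not a demonstrated gap. There is one schedule, with a diary row at every visit. V.E says that usual care is seen on the same schedule as the program arm. The unrestricted diary sentence in V.H stands in the section that promises usual care equal contact. That much stands: a reader might infer that usual care keeps no diaries, and the documents do not establish this. They fail to show that it does, while the only text that names an arm names the other one.

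Three further replies have force.

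- *The scoring rule may exist.* V.D says that all scales are appended, and those appendices are not in the public text. A reader might conclude that no yes/no rule was ever written. The most that can be said is that none is visible. V.I says that the interventions needed to achieve change will be tallied for analysis, but a tally is not a responder rule.
- *Other measures could carry the test.* V.N.3 proposes a linear time trend, so data at months 0, 6 and 12 could support a comparison of slopes, and the fidelity checklist's gap at 8 weeks is not fatal in itself. However, the checklist is not named in Statistical Plans and its arm is not stated. The exit interview gives one time point.
- *The plan does not score absent diaries as no change.* V.N.2 and Statistical Plans treat absent data as missing. A reader might take the Step 4 figures as expected bias. They are a worst case under a rule that no passage prescribes.

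**Conclusion.** The point holds in a conditional form. The plan rests a primary between-arm comparison chiefly on a measure that its arm-specific text gives to one arm. If that text is followed, usual care supplies no comparable diary data, and any diaries from patients who enter the program late would be selected and contaminated. The diary-based comparison could then not be made validly. If both arms keep diaries in the same way, the defect shrinks to reconciling the named measures and stating the yes/no rule.

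No single bias figure can be given. The upper bound, under the unstated rule that an absent diary means no change, is the true usual-care change rate, scaled down by incomplete program diaries.

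A reader might also infer that the trial's main results are compromised. They are not: weight and metabolic outcomes do not depend on diaries. Confidence is medium, because the appended scales and manuals could not be seen.

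**What to change.** 1. In I.D.1(b) and in Statistical Plans (b) and (c), name one lifestyle-change measure, collected the same way in both arms at baseline, 8 weeks, 6 months and 12 months. Fix the yes/no rule before analysis and analyse by randomized arm.
2. Consider the Lifestyle Habits Questionnaire for this role. The schedule already marks it at baseline and every later visit, with no arm restriction shown. First confirm from the appended scales that it covers both diet and exercise and is given in both arms.
3. State in V.E and in the schedule whether usual care keeps diaries. An arm column would do this.
4. Use diaries for the between-arm test only if they are collected alike in both arms. Otherwise use them only to describe adherence to the program.

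The cost is wording in three sections, a schedule column and a scoring rule. No new visit is needed, and no new form if the questionnaire proves suitable. The downside is reliance on questionnaire self-report.

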E. Procedures for the Usual Care Group: As most psychiatrists are being advised to counsel patients on weight, diet, and exercise, Usual Care will be only some modest counseling. Referral to the MOVE program by their treating psychiatrist would not be discouraged. Patients will be encouraged to exercise and eat a healthy diet, and will be weighed at each visit. No classes on nutrition and no exercise classes will be given to these patients as part of this program. Patients in usual care will be seen on the same schedule as the experimental group, in order to equalize contact time. At every visit, patients will complete a questionnaire about their knowledge of healthy eating habits and nutrition. After 6 months, if patients in the “usual care group” wish to participate in the more rigorous behavioral weight loss program they will be given that opportunity. A de-identified photograph of each participant’s body from the neck down will be taken during visit one and at the end of study.

SCHEDULE OF EVENTS

Visit	Time	Rater	0	1-7	8	9	10	11	12	13	14	15	16	17	18
Week			0	1-7	8	12	17	21	26	30	34	38	43	48	52
Month			0		2	3	4	5	6	7	8	9	10	11	12
Visit Log/Assessment Packet	--	--	X	X	X	X	X	X	X	X	X	X	X	X	X
AHA Exercise Risk Stratification	10	MD	X												
Brief Psychiatric Rating Scale (BPRS)	15	MD	X		X				X						X
CGI	5	MD	X		X				X						X
Hamilton Depression/ Beck Anxiety Scale	20	MD	X		X				X						X
Physical Exam	15	MD	X												X
Structured Clinical Interview for DSM-IV (SCID)	15	MD	X												
Antipsychotic Side-effects Checklist (ASC)	5	C	X		X				X						X
Assessment of Patient Food Preparation Activity	5	C	X		X				X						X
Biopsychosocial/Spiritual Wellness Self Appraisal (BPSS)	5	C	X		X				X						X
Demographics	10	C	X												

EXIT interview	5	C														X
Fidelity Checklist Change Assessment	10	Proj. Mgr	X						X							X
Framingham Hard Coronary Heart Disease	5	C	X													X
Healthy Lifestyle Balance Knowledge Quiz	15	C	X		X				X							X
Informed Consent Video	30	--	X													
Informed Consent Quiz	15	C	X						X							X
Labs: Lipid Profile, fasting glucose, HgbA1C, insulin/ HOMA calculation, c-reactive protein, microalbumin, creatinine	10	Lab	X		X				X			X				X
Lifestyle Habits Questionnaire	10	C	X	X	X	X	X	X	X	X	X	X	X	X	X	X
Motivational Interview	5	C	X		X				X							X
Quality of Life Scale	15	C	X													X
SAIQ- Insight Measure	10	C	X		X				X							X
Telephone Contact Assessment (as needed)	5	C														
Treatment Adherence Log	5	C	X		X				X							X
URICA Motivational Scale	10	C	X						X							X
Vitals: Weight, BMI, Waist, %Fat	10	C	X	X	X	X	X	X	X	X	X	X	X	X	X	X
Lifestyle Balance Classes	60	RD	X	X	X											
Lifestyle Balance Booster classes	60	RD				X	X	X	X	X	X	X	X	X	X	X
Personal Goal Sheet	10	RD	X	X	X	X	X	X	X	X	X	X	X	X	X	X
Eating Behavior & Exercise Adherence – additional interventions	2	RD		X	X	X	X	X	X	X	X	X	X	X	X	X
Caregiver dietary Information Session	60	RD	X			X			X			X				X
Food and Exercise Diary	15	RD	X	X	X	X	X	X	X	X	X	X	X	X	X	X
Exercise Tolerance Test	120	C	X													
Electrocardiogram	15	C	X													

Example Schedule for Lifestyle Balance Classes and Exercise Opportunities at West Los Angeles Site

Day of Week	Mon	Tue	Weds	Thurs	Fri
AM Class	Cohort 1	Cohort 2	Cohort 3	Cohort 4	Cohort 5
PM Class	Booster	Booster	Booster	Booster	Booster
Day of Week	Monday	Tuesday	Wednesday	Thursday	Friday
Exercise Options offered at PRRC:	Walking Group 11:00am Yoga 1:00pm	Physical Fitness 8:00am Yoga 1:00pm Golfing 2:00pm	Yoga 2:00pm	Thai Chi 9:00am Field Trip 10:00am (eg farmers market, museum)	Yoga 1:00pm

				walking)	
Exercise option Rehab wellness clinic	Daily available stationary bicycle and weight lifting	Daily available stationary bicycle and weight lifting	Daily available stationary bicycle and weight lifting	Daily available bicycle and weight lifting	Daily available bicycle and weight lifting

G. Study Assessments:

1. Screening and General Medical Procedures: The process of obtaining informed consent will culminate in a quiz on the details of the project and participating in research, which is repeated at 6 and 12 months. During the first visit, patients will have a comprehensive physical exam and psychiatric interview. An electrocardiogram and demographics will be recorded. Framingham risk assessment for cardiovascular disease will be calculated and repeated at the end of the study. Routine vital signs, blood pressure, and pulse will be measured at each visit. Patients at high risk for cardiovascular disease and/or current symptoms of angina may need referral for an exercise tolerance test before embarking upon the exercise component of this behavioral weight loss program. [name], our co-investigator in charge of the outpatient rehabilitation medicine department, has agreed to assist us with expediting exercise tolerance tests for patients wishing to participate in exercise as part of their weight loss plan.

2. Weight Loss Measures: Weight loss measures including measurement of weight, body mass index (BMI), waist circumference, and body composition (% body fat) will occur at each visit of the study. Weight will be obtained on the same clinic scale for all patients. All weight measurements will occur at the same time of day for each appointment. Height measurement will be made at the first screening appointment to calculate BMI. The measurement of the 'waist' is taken at the point midway between the iliac crests and the costal margins. Measurement of the waist is thought to reliably relate to cardiovascular risk, as it reflects visceral adiposity (66) and can assist in diagnosis of the metabolic syndrome. A waist measurement of 35 inches or greater is part of the diagnostic criteria for the metabolic syndrome diagnosis for women and greater than 40 inches meets diagnostic criteria for men. Percent body fat analysis will be performed using a small machine that patients hold in their hands for one minute. This machine emits an electromagnetic signal that uses the differential impedance of bodily tissues to calculate percent body fat. Patients using pacemakers cannot use this device because of concerns of possible interference.

3. Laboratory Measures: Laboratory measures that include hemoglobin A1c, fasting blood glucose, cholesterol, triglycerides, c-reactive protein, and insulin to determine insulin resistance as calculated by the HOMA method. Urine will be collected and tested for diabetes. Laboratory tests will be completed at 3-month intervals.

4. Psychiatric Assessments: These measurements are being done to assess the impact of the behavioral program on overall psychiatric condition as well as the psychiatric factors that impact weight loss. Formal psychiatric assessments will be done at baseline at the end of the 8 weeks of classes, 6 months, 12 months, and end of study. Quality of life will be assessed at baseline and end of the study.

a) Brief Psychiatric Rating Scale (BPRS): The BPRS is a 24 item scale that assesses many aspects of psychopathology including positive psychotic symptoms, (hallucinations, paranoia, unusual thought content and conceptual disorganization) as well as symptoms of anxiety and depression (67). The BPRS will be used to screen positive, negative, and cognitive symptoms that might impact patients' ability to lose weight (15 minutes).

b) Clinical Global Improvement Scale (CGI) The CGI is a 7-point scale that measures the severity of a patient's psychiatric illness as well as improvement compared to baseline. (5 minutes)

c) Quality of Life Interview- Brief Version (Heinrichs): This interview scale has become standard in the field of assessing the quality of life from the perspective of a patient with SMI. The scale will be administered at baseline and at the end of one year (68). (15 minutes)

d) Cognitive Assessments: The cognitive screening we will use in this study will be the summary score of the cognitive items on the BPRS and the Self Appraisal of Illness Questionnaire (SAIQ) will measure the level of insight into psychiatric and medical condition. These tests will be assessed at baseline, 8 weeks, 6 months, 12 months, and at end of the study (69). (20 minutes).

e) Hamilton depression scale: This 18 item scale will be administered at baseline, 8 weeks, 6 months, 12 months, and at the end of the study.

f) Motivation Assessment: Behavioral treatment of problem behaviors involves helping patients with their motivation to change. Five stages of change have been conceptualized for a variety of problem behaviors. The five stages of change are precontemplation, contemplation, preparation, action, and

maintenance. Precontemplation is the stage at which there is no intention to change behavior in the foreseeable future. Many individuals in this stage are unaware or underaware of their problems. Contemplation is the stage in which people are aware that a problem exists and are seriously thinking about overcoming it but have not yet made a commitment to take action. Preparation is a stage that combines intention and behavioral criteria. Individuals in this stage are intending to take action in the next month and have unsuccessfully taken action in the past year. Action is the stage in which individuals modify their behavior, experiences, or environment in order to overcome their problems. Action involves the most overt behavioral changes and requires considerable commitment of time and energy. Maintenance is the stage in which people work to prevent relapse and consolidate the gains attained during action. For addictive behaviors this stage extends from six months to an indeterminate period past the initial action. Most of the patients who will join this study will do so presumably, because they are at the Action stage in this hierarchy. Patients' motivational state will be assessed at baseline, 8 weeks, 6 months, 12 months, and end of study utilizing the URICA, a validated and reliable measure of motivation (70).

g) Biopsychosocial/spiritual Wellness Self Report Scale. To measure the sense of wellness the patient has in biological, psychological, social and spiritual realms, this scale is a 4 item scale with a maximum of 10 points per item reflecting level of wellness that the patient feels.

H. Adherence Methods: Each patient will be assigned a lifestyle balance coach/case manager. The model we use in our treatment of patients is intensive case management and a minimum of bimonthly contacts for each patient. Patients assigned to the "usual care" group will also have case managers and equal contact so that contact time will be equal for each group. We have had extensive experience with utilizing a case management approach with all of our previous clinical trials, and successfully used during our current merit review program. The diabetes prevention program that has been adapted for this protocol has an extensive operations manual that has a long section devoted to methods of improving adherence to the Lifestyle Balance program. Please see appendix of this grant for our operations manual and particularly the "toolbox" section for helping patients adhere to the Lifestyle Balance program.

Adherence is dependent, in part, on environmental and caregiver influences. Many of our patients have little influence over the food that is fed to them in board and care homes. We will assess patient's involvement in food preparation and their willingness to involve their caregivers in helping make necessary dietary changes. Our Lifestyle Balance coaches will act as a liaison to patients' caregivers, family, and or board and care operators and will provide on-site nutritional and cooking education and to assist these care providers with understanding the dietary needs of the patients involved with our behavioral program. In some cases, we may need to recommend meal replacements such as Slimfast when patients are having difficulty with portion control. Patients' participation in their own food preparation will be assessed initially as well as their willingness to have us contact their caregivers to provide support and education towards the dietary goals of this program. Our patients will be asked to provide a food and exercise diary. If patients are having difficulty with losing weight, they will be asked if they would be willing to allow a case manager to attend their meals for a few days to assist them in making healthy choices.

Adherence to the Lifestyle intervention and fidelity of the lifestyle balance coach as well as the patient, will be checked with a specially designed instrument that helps assess lifestyle balance intervention adherence and prompts the lifestyle balance coaches to make necessary suggestions for patients having difficulty making lifestyle changes.

I. Exercise Opportunities: Over the past three years of funding, at the West Los Angeles site, we have made arrangements for innovative exercise opportunities that are enjoyable and thus, enhance adherence to the program. Exercise groups are available every day in the PRRC to increase convenience for the patients. Patients will also be able to go to an introductory 12-week long exercise program on the VA grounds called the Wellness program in the department of rehabilitation medicine, and utilize exercise equipment there. Wellness programming is also available at the Sepulveda and Long Beach sites. Part of the duties of study personnel will be to identify and develop daily exercise opportunities at the 3 other sites. Over the first 6 months of the start up time for funding these opportunities should be developed. In cases where patients require an ETT and exercise in a monitored setting, [name] or other designated Physical Medicine and Rehabilitation physician will advise individual exercise programs. Similarly, if people are having difficulty adhering to the exercise regimen we will make every effort to assist them in finding a way to make their exercise goal. In work that we have done in the past, we have found that in-vivo assisted skills training is beneficial to patients with schizophrenia.

This population will not respond well to authoritarian treatment but will respond well to consistent positive reinforcement for every bit of progress. Positive reinforcement is crucial. We will temper our

expectations and applaud any and all positive movement. Patients with low level of motivation will be rewarded with positive affirmations for merely attending the class consistently as an achievement, thus seeing changes in the patients' attitudes, behaviors, and even some weight loss.

Lifestyle Balance Coaches and physicians will meet as a team to discuss patients who need additional interventions to meet their expected dietary changes and exercise goals. We have developed a flow chart that our Lifestyle Balance Coaches will utilize to assist patients with adherence to the program. The number and types of interventions required to assist patients in making healthy lifestyle changes will be tallied. For the most part, these are the modalities described in the grant that can be ascertained in an objective manner for data analysis purposes. Lifestyle coaches' adherence to the training program will be assessed by a simple fidelity measure and an independent objective consultant who will randomly observe coaches meeting with veterans in the lifestyle balance intervention group.

Because weight gain can be a deterrent for patients to adhere to antipsychotic medications, one of our hypotheses is that people in the lifestyles intervention group will have higher rates of adherence to their psychiatric medications than patients in the "treatment as usual" group. We will rely primarily upon the VA computerized record system to determine the percent of psychiatric appointments attended by patients as well as the percent of medications refilled. In addition, we have developed and will utilize several objective measures of adherence to treatment.

J. Additional Interventions: In the event that the patient is not losing weight or is unable to adjust to their diet or exercise regimen, we will request the patients permission for additional intervention so that we may assist them adhere to their exercise and diet. Additional interventions are optional and may include:

1. Additional Exercise Interventions

- a. The research physician will review the patient's medical chart to determine if their current medications may be contributing to fatigue, sedation, and/or lack of motivation. Consultation with the patient's treating psychiatrist may lead to suggestions about medication adjustments to be made by the treating psychiatrist (as it would be done in usual care) to optimize energy and motivation of patients.
- b. The patient's rewards may be adjusted to optimize their motivation to exercise (See DPP Toolbox Appendix).
- c. The patient's exercise goal expectations may be adjusted.
